## 9.0 STATISTICAL CONSIDERATIONS AND DATA MANAGEMENT

### 9.1 General Considerations

To test our hypotheses, we will use intention-to-treat (ITT) analysis of covariance models to test for treatment group differences in Week 24 levels of inflammation biomarkers adjusted for baseline levels. P-values will be two-sided and considered significant at  $\alpha=0.05$ . Adjustments for multiple comparisons will not be performed due to the relatively small sample size and exploratory nature of this phase II trial.

In secondary/exploratory analysis, multivariable linear regression models will be constructed to include treatment group and other potentially confounding baseline and time-updated variables that differ significantly between groups and which may account for differences in outcomes. Baseline characteristics that may be included in the models are demographics (age, sex, race/ethnicity), ISI scores, PHQ-9 and SCL-20 scores, tobacco/adherence questionnaire results, ART drugs/regimens (including efavirenz, rilpivirine, and integrase inhibitors), insomnia medication use, comorbidities, CD4 cell counts, HIV-1 RNA levels, levels of the inflammation biomarkers, and nonprescription substance use. Time-varying characteristics that may be included are changes in ISI scores, questionnaire results, CD4 cell counts, ART drugs/regimens, and HIV-1 RNA levels.

We will also perform ‘per protocol’ secondary analyses comparing the ISI4-6 subgroup (defined as participants who completed  $\geq 4$  of the 6 SHUTi sessions) vs. the active control group to determine if greater SHUTi engagement leads to greater differences in the endpoints of interest.

We will also examine relationships between changes in questionnaire scores, especially ISI scores, and the inflammatory endpoints using Pearson correlations.

All of these models will be repeated for comparing 12-week changes in the endpoints in addition to the primary models for 24-week changes.

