### DESIGN

The objectives of this study will be met by conducting a 24-week, single-center, single-blinded, two-arm, parallel-group, randomized, controlled pilot trial. A total of 250 participants may be screened to identify the 50 participants who will be randomized into this pilot trial. We aim to enroll at least 25% women into this trial, or 12 of the 50 to be randomized. These participants will be randomized 1:1 (stratified by sex and current use of sleep aids/medications) to either the internet CBT-I program SHUTi (N=25) or an internet sleep education/hygiene Active Control (N=25). Four study visits are required (Screening, Entry, Week 12, and Week 24).

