### 3.3 Entry/Randomization Visit

Participants will be scheduled for this Entry/Randomization Visit within 42 days of the date of the positive ISI score criterion. This visit will occur at the Infectious Diseases Research Clinic located at the Fifth Third Office Building on the Eskenazi Hospital campus.

The study team will first undergo with the participant the written, informed consent process. A random study code number will be assigned to the participant to ensure confidentiality. This study code number will be used for result reporting and data recording.

For women of reproductive potential, a urine pregnant test (UPT) will then be performed before randomization and other required study procedures. If the UPT is positive, study participation will end. Otherwise, randomization and the other study procedures for this visit will continue. Randomization will be stratified by sex at birth (male/female) and by current regular ( $\geq 2$  times/week) use of prescribed or over-the-counter sleep aids/medications (yes/no) using random number sequences. Sequentially numbered, opaque, sealed envelopes containing treatment assignment will be prepared by the study statistician.

At this visit, updated medical/psychiatric records, current medications, and current behavioral therapies will be reviewed and recorded. Height, weight, and vital signs will be measured and recorded. All participants will complete a questionnaire battery containing the following: standard questions assessing demographics, medical/psychiatric history, sleep mediation use, insomnia treatment satisfaction, and insomnia care received outside of the trial; ISI; PSQI; DBAS-16; PHQ-9; SCL-20; GAD-7; PROMIS® Fatigue Short Form; AUDIT; PEG-3; and SF-36. The questionnaire battery will also include validated scales assessing physical activity level, tobacco use, illicit drug use, medication adherence, and the probability of sleep apnea (STOP-BANG Questionnaire (94)). The questionnaire battery will be administered on a computer in private with availability of the study team to assist only when asked by the participant. The participant may refuse to complete any of the questionnaire items.

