## 5.2 The Active Control Group: Internet Sleep Education/Hygiene, Symptom Monitoring, and Usual Care.

In our pilot trial, our comparator was usual care. However, in the proposed trial, we will use an active control comparator (107) for two reasons. First, we wish to obtain precise effect size estimates for the next-step trial, and a usual care comparator could overestimate efficacy. Of note, Irwin's RCT (21) found moderate-to-large improvements in insomnia remission and CRP with CBT-I versus a sleep education/hygiene active control. Second, our active control arm will help to ensure that the groups have similar expectancy of benefit.

The Active Control RA, another clinical psychology PhD mentee of [name], will oversee and deliver the active control procedures. First, the RA will give participants access to the internet sleep education/hygiene program, which was created by our consultant, [name], to serve as a standardized active control condition for SHUTi. This educational program was developed at the University of Virginia with funding from the National Institutes of Health and is fully accessible via tablets and smartphones. This program provides static information about: insomnia symptoms; the impact, prevalence, and causes of insomnia; when to see a doctor; and basic lifestyle, environmental, and behavioral strategies to improve sleep (i.e., sleep hygiene recommendations). Of note, participants in our trial will not enter any identifying information into the internet sleep education/hygiene program other than the email address they choose to use to receive messages (e.g., reminders) from the program. The content for this program was informed based on a review of insomnia-focused websites at the time of development. Second, just after giving participants access the internet sleep education/hygiene program, the RA will email or mail a list of local behavioral health services to patients and will encourage them to follow-up with their HIV provider. To engender expectancy of benefit, the RA will stress that our notifications should prompt actions by their provider and that the available treatments are evidence-based. We will then notify the HIV provider, which will encourage them to address their patient's

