### 9.2 Missing Data Approach

Missing data mechanisms will be examined by comparing completers with incompleters on the baseline factors. Multiple imputation (SAS proc mi and mianalyze) will be used if a substantial amount ( $>10\%$ ) of missing data exist. If differential missing patterns are observed, sensitivity analyses will be performed to evaluate the consequences of potential missing mechanisms.

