### 9.3 Potential Moderators, including Biological Sex, of Intervention Effects

In exploratory analyses, we will test interactions between the following baseline factors and treatment group to examine these factors as potential moderators of intervention effects: age, sex, inflammation biomarkers levels, ISI scores, PHQ-9 and SCL-20 scores, use of sleep aids/medications, and nonprescription substance use. Given that the proposed trial is not powered to detect such interactions, specific models will also be run separately for males and females to assess whether there are clinically important differences in the treatment group-outcome relationships between sexes.

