#### 9.5 Sample Size Justification

The goal of this application is to provide proof-of-concept data and effect sizes of SHUTi on inflammation/monocyte activation endpoints in support of a future, definitive trial. As such, the proposed sample size is based on the enrollment time period and the funding allowance of the R21 mechanism, not for definitive superiority testing. We will enroll 50 participants with the expectation that 40 (20 in each arm) will complete the 24 week study. Using the standard deviations and correlations between baseline and week 24 for hsCRP (this trial's primary endpoint) from our previously published depression trial, we have 80% power ( $\alpha=0.05$ ) to detect mean differences between study groups of 3.41 mg/L. This detectable difference is clinically meaningful, as it is similar to that found to be predictive of CVD events and overall mortality in the SMART trial (66, 110).

For the primary and secondary endpoints, the following table demonstrates the effect sizes that can be observed between study groups (N=20 in each arm), assuming similar variances and correlations as observed in our pilot trial of internet CBT for depression in PWH. Of note, the detectable difference in IL-6 is also clinically meaningful, given that differences of 1.3-2.2 pg/mL were associated with greater risks of CVD and mortality in the SMART trial (66, 110).

Outcome	SD	Correlation	Detectable mean difference (N=20 per group)
hsCRP (mg/L)	4.87	0.64	3.41
IL-6 (pg/mL)	2.34	0.32	2.02
sCD14 (ng/mL)	751	0.70	488
sCD163 (ng/mL)	19.12	0.89	7.97
%CD14+CD16+ monocytes	5.54	0.31	4.77

Our group has access to ~3000 HIV-positive outpatients engaged consistently in care within the Indiana University Health system (Eskenazi Health with 1200; IU Methodist Hospital with 1800). As part of our pilot trial, we found that ~30% of the virologically-suppressed PWH in our HIV clinics have ISI scores  $\geq 11$ . Thus, there are ~900 patients eligible for recruitment. Based on review of our clinic population characteristics, we estimate ~800 will fulfill the other eligibility criteria.

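### The primary ANCOVA leaves out the two stratification factors; adding them is a cheap improvement that gains precision if they are prognostic and costs little if they are not

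*Protocol*

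**What the plan says.** The Design paragraph of the Schema has participants randomised 1:1, "stratified by sex and current use of sleep aids/medications". Protocol 3.3 gives the detail: "Randomization will be stratified by sex at birth (male/female) and by current regular" (at least twice a week) "use of prescribed or over-the-counter sleep aids/medications (yes/no) using random number sequences". That makes four cells. Whether blocks are used within them is not stated.

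The analysis for the biomarkers, hsCRP at Week 24 being primary, is an intention-to-treat ANCOVA to "test for treatment group differences in Week 24 levels of inflammation biomarkers adjusted for baseline levels" (Protocol 9.1; the SAP uses the same words under Statistical Analyses). The only covariate named is the baseline value of the biomarker.

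The stratification factors appear in two other places, neither of them the primary test:

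- Protocol 9.1 and the SAP list demographics and insomnia medication as candidates for secondary multivariable models, for variables that differ significantly between the arms.
- Protocol 9.3 covers moderators: "In exploratory analyses, we will test interactions between the following baseline factors and treatment group". Sex and sleep-aid use are both on that list, and models are also run separately by sex. The SAP has the sex part only.

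**The concern.** A factor used to stratify the allocation would normally also be in the analysis model. If it predicts the outcome beyond baseline, adjusting for it removes residual variance. If allocation is also balanced within strata, a model without it ignores balance that the design created: its standard error is too large and its test somewhat conservative.

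This matters here because the trial's product is an estimate. Protocol 5.2 justifies the active control by saying "we wish to obtain precise effect size estimates for the next-step trial".

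The secondary models do not fill the gap. They are optional and triggered by a significant imbalance, which stratified allocation, if blocked, makes unlikely for exactly these two variables. Interaction tests and sex-specific fits do not give an adjusted primary estimate either.

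**Working it through.** **Inputs from the documents.** hsCRP SD 4.87 mg/L, baseline to Week 24 correlation 0.64, detectable difference 3.41 mg/L at 80% power, two-sided alpha 0.05 (Protocol 9.1 and 9.5). Also from 9.5: "We will enroll 50 participants with the expectation that 40 (20 in each arm) will complete the 24 week study". About 25% women (Protocol 10.7).

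**Assumed, because the documents do not say.** 40% sleep-aid users; q from 0 to 20%, split equally between the two factors; blocks of 4 within strata, or 25:25 with no blocking; dropout at random; normal data.

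**Step 1: the plan's own figure.** Residual SD = 4.87 × √(1 − 0.64²) = 3.742. Standard error with 20 per arm = 3.742 × √(2/20) = 1.183. With a noncentral t on 37 df, the detectable difference is 3.404 mg/L, and power at 3.41 is 80.1%. The stated figure is therefore reproduced, and it belongs to a baseline-only model.

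**Step 2: formula for the adjusted model.** The residual SD becomes 3.742 × √(1 − q), on 35 df:

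| q | Detectable difference (mg/L) | Power at 3.41 |
|---|---|---|
| 0 | 3.410 | 80.0% |
| 5% | 3.323 | 82.0% |
| 10% | 3.235 | 84.0% |
| 20% | 3.050 | 88.0% |

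This puts break-even at q of about 0.3%, which is too favourable. It ignores chance imbalance between arms on the two factors, and it gives the planned model no credit for balance achieved by design.

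**Step 3: simulation allowing for both.** 40,000 trials per setting; 50 allocated, 40 kept at random; true difference 3.41 mg/L for power. Monte Carlo standard error is about 0.2 points for power and 0.1 for type I error. Power changes are adjusted minus planned, in points. A dash means not tabulated.

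| q | Power change, blocks of 4 | Power change, no blocking | Type I error of planned test, blocks of 4 | Mean 95% CI width (mg/L), planned vs adjusted, blocks of 4 |
|---|---|---|---|---|
| 0 | -0.8 | -2.4 | 5.0% | 4.85 vs 4.89 |
| 2% | -0.3 | -1.7 | - | - |
| 5% | +0.9 | -0.2 | 4.6% | - |
| 10% | +2.5 | +1.6 | 4.1% | 4.85 vs 4.64 |
| 20% | +5.6 | +5.8 | 3.3% | 4.85 vs 4.37 |

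Without blocking, the planned test holds 4.9-5.1% at every q, so it is not conservative, and the CI widths at q=0 are 4.84 vs 4.98. The adjusted test stays at 4.8-5.2% throughout. Break-even is at q of about 3% with blocks and 5-6% without. A repeat with 8,000 trials per setting agreed within Monte Carlo error.

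**Step 4: what q means in mg/L.** Suppose the strata differ by the same amount at baseline and Week 24, and let b be the share of total variance that lies between strata. Then

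q = 1 − [(1 − b) − (0.64 − b)²/(1 − b)] / (1 − 0.64²).

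At b = 0.12 the bracket is 0.88 − 0.2704/0.88 = 0.573, and 0.573/0.5904 = 0.97, so q = 3%. With half of b on each factor:

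- women vs men: √(0.06 × 4.87² / (0.25 × 0.75)) = 2.8 mg/L;
- users vs non-users: √(0.06 × 4.87² / (0.40 × 0.60)) = 2.4 mg/L.

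The same calculation gives about 3.4 and 3.0 mg/L for q=5%, 4.4 and 3.9 for 10%, and 5.5 and 4.9 for 20%.

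**The case against.** The strongest reply is that the gain is hypothetical. The documents offer no evidence that sex or sleep-aid use predicts Week 24 hsCRP once baseline hsCRP is in the model, and baseline already absorbs much of any stable difference. Step 4 shows that the upper rows of the table need differences between strata as large as, or larger than, the 3.41 mg/L the plan calls clinically meaningful, unless the differences change over time. Below break-even the change loses power. A parsimonious model is defensible with 40 completers in a trial that Protocol 9.5 says is not sized for definitive superiority testing. The simulation also assumes normal, complete data, whereas the plan allows transformation or nonparametric tests and expects enough loss to trigger imputation.

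Most of this stands. The q=20% row should be read as an upper bound, the net benefit at small q is slightly negative, and q would differ on a transformed scale. What it does not do is remove the case for the change. The loss is bounded at about 1 point of power with blocks or 2.4 without, the baseline-only model can still be reported, and the sponsor considered these two factors important enough to stratify on and to list as moderators. Not being sized for superiority testing makes precision more relevant, not less.

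**Conclusion.** The concern holds as a conditional, low-cost improvement. Neither document puts the stratification factors in the primary ANCOVA or gives a reason for leaving them out. The planned analysis is valid: nothing here biases the estimate or inflates type I error, and 3.41 mg/L is correct for the model as written.

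With assumed blocks of 4, the effect of adding the factors runs from a loss of 0.8 points of power and a CI about 1% wider (q=0) to a gain of 5.6 points and a CI about 10% narrower (q=20%; 4.37/4.85 = 0.90). Without blocking, the loss at q=0 is 2.4 points and the CI about 3% wider (4.98/4.84 = 1.03). These figures rest on the assumed q, 40% sleep-aid use, random dropout and a complete-case analysis on an untransformed, normal scale. Multiple imputation was not simulated. Because the sign of the effect depends on an unknown q, the choice should be fixed before unblinding.

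**What to change.** In Protocol 9.1 and the SAP's Statistical Analyses, specify the biomarker ANCOVA as: Week 24 (or Week 12) level = treatment + baseline level + sex at birth + baseline regular sleep-aid use, with the two factors as main effects. Name the baseline-only ANCOVA as a sensitivity analysis.

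Two consequences should be handled in the same edit:

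- Protocol 9.2 says "Multiple imputation (SAS proc mi and mianalyze) will be used if a substantial amount" (above 10%) is missing. The expected loss is 10 of 50, or 20%, so the imputation model should include the same two factors as the analysis model.
- State whether allocation is blocked within strata, since the size of the gain or loss depends on it. Block sizes can stay out of the protocol.

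The cost is a sentence in each document and two degrees of freedom. No new data are needed, since both variables are recorded for the randomisation.

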### 1.2 Secondary Objectives

1.2.1 To compare 12-week changes in hsCRP levels between those undergoing SHUTi vs. Active Control.

1.2.2 To compare 12- and 24-week changes in levels of IL-6, sCD14, sCD163, and CD14+CD16+ monocytes between those undergoing SHUTi vs. Active Control.

1.2.3 To compare 12- and 24-week changes in Insomnia Severity Index (ISI), Pittsburgh Sleep Quality Index (PSQI), Dysfunctional Beliefs and Attitudes about Sleep (DBAS-16), sleep mediation use, insomnia treatment satisfaction, Patient Health Questionnaire-9 (PHQ-9), Hopkins Symptom Checklist (SCL-20), Generalized Anxiety Disorder-7 (GAD-7), PROMIS® Fatigue Short Form, Alcohol Use Disorders Identification Test (AUDIT), Pain, Enjoyment, General Activity Scale (PEG-3), and Short Form-36 (SF-36) Health Survey between those undergoing SHUTi vs. Active Control.

1.2.4 To evaluate potential treatment effect moderators including the following baseline factors: age, ISI, insomnia pharmacologic treatment, depression status, substance use, and hsCRP level.

1.2.5 To evaluate the potential treatment mediating effects of insomnia symptom severity, behavioral changes, and HIV virologic rebound on inflammation biomarkers.

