## 2.0 HYPOTHESES, SIGNIFICANCE, AND BACKGROUND

### 2.1 Hypotheses

2.1.1 Insomnia treatment with SHUTi will reduce circulating hsCRP compared to sleep education/hygiene Active Control at 24 weeks.

2.1.2 Insomnia treatment with SHUTi will reduce circulating hsCRP at 12 weeks and IL-6, sCD14, sCD163, and CD14+CD16+ intermediate monocyte levels at both 12 and 24 weeks compared to sleep education/hygiene Active Control.

2.1.3 Insomnia treatment with SHUTi will reduce ISI scores at 12 and 24 weeks compared to sleep education/hygiene Active Control.

2.1.4 Effects of insomnia treatment with SHUTi on inflammation may be moderated by baseline factors including age, ISI, insomnia pharmacologic treatment, depression status, substance use, and CRP level, and may be mediated by insomnia symptom severity, behavioral changes, and HIV virologic rebound.

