#### 9.4 Mediation Analyses

Preliminary mediation analyses to assess for intervention-related decreases in ISI scores, behavioral changes, and HIV virologic rebound (either singly or in combination) to explain reductions in the inflammation/monocyte activation endpoints will be performed.

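### The secondary adjusted models can treat post-randomisation change in ISI as a confounder, although the protocol names insomnia severity as a potential mediator

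*Protocol*

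**What the plan says.** The primary analysis is an intention-to-treat ANCOVA to "test for treatment group differences in Week 24 levels of inflammation biomarkers adjusted for baseline levels". Protocol 9.1 then describes secondary/exploratory multivariable regressions containing treatment group and "other potentially confounding baseline and time-updated variables that differ significantly between groups and which may account for differences in outcomes". The candidates are spelled out: "Time-varying characteristics that may be included are changes in ISI scores, questionnaire results, CD4 cell counts, ART drugs/regimens, and HIV-1 RNA levels". The SAP (Statistical Analyses) carries both sentences in the same words. The models are run at both time points: "All of these models will be repeated for comparing 12-week changes in the endpoints".

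Elsewhere the protocol gives insomnia severity a different role:

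- Hypothesis 2.1.3 expects SHUTi to lower ISI at 12 and 24 weeks.
- Objective 1.2.5 is "To evaluate the potential treatment mediating effects of insomnia symptom severity, behavioral changes, and HIV virologic rebound on inflammation biomarkers".
- Hypothesis 2.1.4 says the effects on inflammation "may be mediated by insomnia symptom severity, behavioral changes, and HIV virologic rebound".
- Section 9.4 plans "Preliminary mediation analyses to assess for intervention-related decreases in ISI scores, behavioral changes, and HIV virologic rebound".

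Section 9.5 gives the purpose of the trial as "to provide proof-of-concept data and effect sizes of SHUTi on inflammation/monocyte activation endpoints in support of a future, definitive trial".

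**The concern.** One variable has two incompatible roles. In a randomised comparison, a change that treatment brings about after randomisation is not a confounder of the treatment effect. If ISI lies on the path from SHUTi to hsCRP, conditioning on its change removes the part of the effect that runs through it. If ISI change and hsCRP also share unmeasured causes, conditioning on it can move the treatment coefficient in either direction, even when nothing is mediated.

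The entry criterion makes this more likely. A variable qualifies by differing significantly between arms, so ISI change is most likely to qualify when SHUTi works on insomnia. Neither document says that the resulting coefficient is not a total effect, and neither rules out its use in planning the later trial. What is at stake is a biased secondary estimate presented as control of confounding.

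The same overlap exists, less directly, for HIV-1 RNA (virologic rebound) and questionnaire results (behavioural changes). Neither can be sized, because the documents give no rebound rate and do not define the behavioural measures.

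**Working it through.** **Inputs from the documents.** hsCRP SD 4.87 mg/L, baseline-to-week-24 correlation 0.64, 20 completers per arm, two-sided alpha 0.05, 80% power, detectable difference 3.41 mg/L (9.5). Effects on ISI: d = 0.82 at 10 weeks against usual care, from a pilot with 6 and 8 completers (2.3.3); d = 1.10 at 6 weeks and 0.83 at 6 months in the cited 1,149-person trial against an internet attention control (2.2.4).

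**Assumptions.** d = 0.3 and 0.5 as smaller effects; the share of the hsCRP effect mediated by ISI (25% or 50%); a residual correlation of ±0.3 between ISI change and hsCRP. The documents give neither mediated shares nor this correlation.

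**1. The plan's own figure.** ANCOVA residual SD = 4.87 × √(1 − 0.64²) = 3.74 mg/L. The standard error of the difference is 3.74 × √(2/20) = 1.18. Noncentral-t power with 37 df gives a detectable difference of 3.40 mg/L, and power of 80.1% at the stated 3.41. The planning figure therefore belongs to the baseline-adjusted ANCOVA.

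**2. Chance that ISI change differs significantly.** Two-sample t-test, 38 df, noncentrality d × √(20/2): 15% at d = 0.3, 34% at 0.5, 72% at 0.82, 73% at 0.83, 92% at 1.10.

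**3. Expected coefficient with ISI change always in the model.** With no shared causes, it is total × (1 − mediated share): −3.41 × 0.75 = −2.56 and −3.41 × 0.50 = −1.71. With no mediation and residual correlation ρ, the shift is ρ × 3.74 × d. At ρ = 0.3 and d = 0.83 this is 0.93, giving −2.48, or −4.34 for ρ = −0.3.

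**4. Adding ISI change only when it is significant.** Simulation with 20,000 trials per scenario, total residual SD fixed at 3.74, Monte Carlo SE about 0.01. True total effect −3.41, used only as a scale. Mean treatment coefficient (mg/L):

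| ISI effect d | 25% mediated | 50% mediated | None mediated, ρ = +0.3 | None mediated, ρ = −0.3 |
|---|---|---|---|---|
| 0.3 | −3.07 | impossible | −3.28 | −3.54 |
| 0.5 | −2.93 | not shown | −3.09 | −3.74 |
| 0.83 | −2.70 | −1.98 | −2.63 | −4.20 |
| 1.10 | −2.59 | −1.76 | not run | not run |

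In the trials at d = 0.83 where ISI change is selected, the mean is −2.57 (25%) or −1.72 (50%). The treatment coefficient is significant in 79–80% of trials without ISI change, and in 55% (25%) or 39% (50%) when this selection is applied.

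**5. How strong the assumptions are.** The residual correlation of ISI change with hsCRP implied by a mediated share is 3.41 × share / (d × 3.74). For 25% it is 0.76, 0.46, 0.27 and 0.21 at d = 0.3, 0.5, 0.83 and 1.10. For 50% it is 0.91, 0.55 and 0.41 at d = 0.5, 0.83 and 1.10, and above 1 at d = 0.3. So 25% at d = 0.3 is already a strong assumption, and 50% is shown only for d of 0.83 or more.

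**6. True effect zero, ρ = +0.3.** The mean coefficient is +0.79 with 9.6% rejection at d = 0.83, +0.32 with 5.5% at d = 0.5, and +0.13 with 4.8% at d = 0.3.

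**7. No mediation and no shared causes, d = 0.83.** The mean is −3.40, so there is no bias. The mean standard error rises from 1.19 to 1.31.

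**The case against.** **Inclusion is optional.** The text says variables may be included, and it sets a second, judgemental condition: that the variable may account for outcome differences. Nothing prescribes automatic entry at p < 0.05. This stands. The percentages in step 2 are upper bounds on inclusion, and the table shows what happens if significance alone decides.

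**The models may be meant as explanatory.** They are labelled secondary/exploratory and sit beside correlation and mediation analyses, and no passage says they supply the effect size. That reading is possible. But the text calls these variables potentially confounding, and mediation has its own section. If explanation is intended, a label settles it.

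**The scale is generous.** The one hsCRP difference for internet CBT in people with HIV that the protocol reports is −1.18 mg/L (95% CI −3.50 to 1.14; Table 1, against usual care). At a true −1.18 the coefficient averages −0.94 (25%) or −0.68 (50%) at d = 0.83, −1.01 (25%) at d = 0.5 and −1.06 (25%) at d = 0.3. These shifts of about 0.1 to 0.5 mg/L compare with a standard error of 1.19, and power without ISI change is only about 16%. This stands for the mediation scenarios. The shift from shared causes does not shrink with the true effect, as step 6 shows.

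**The remedy reaches beyond ISI.** Changes in CD4 count and ART are not named mediators, and the SAP has no mediation section. Both are true. Changes in CD4 and ART are nevertheless measured after randomisation, so they are not baseline confounders either. In the SAP they can go into models labelled explanatory.

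**Conclusion.** The concern holds and should be fixed. As written, the covariate rule can bring a hypothesised mediator into a model described as controlling confounding, and it is most likely to do so when SHUTi improves insomnia. The coefficient would equal the total effect only if ISI change were unrelated to the biomarker given treatment and baseline, or if the biases happened to cancel. The protocol's own mediation hypothesis points the other way.

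The textual conflict is certain; the size of the bias is not. It rests on assumed mediated shares and correlations, and on ISI effects from other trials, one of them a very small pilot against usual care. On the 3.41 mg/L scale at d = 0.83, the loss is about 0.7 mg/L (3.41 − 2.70) at 25% mediated and 1.4 mg/L (3.41 − 1.98) at 50%. With the ±0.3 residual correlation and no mediation, the shift is at most about 0.1 mg/L at d = 0.3. The primary test, the sample size and the power statement are untouched.

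**What to change.** In Protocol 9.1 and the matching SAP paragraph, remove the reference to time-updated variables, and the sentence listing the time-varying candidates, from the models that estimate the adjusted treatment effect. Do this for both 12 and 24 weeks, so that these models use baseline covariates only. Which baseline covariates to use is a separate matter.

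Keep post-randomisation changes in ISI, questionnaires and behaviours, HIV-1 RNA, CD4 and ART for the mediation analyses in 9.4 or for models labelled explanatory. Because the SAP has no mediation section, it needs the labelled-explanatory wording or a short new section. Add for those models: *The treatment coefficient in these models does not estimate the total effect and will not be used as the effect size for the later trial.*

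The cost is wording only, with no new data. The downside is that the adjusted effect models would no longer account for post-baseline changes in ART, CD4 or outside care. Section 5.2 leaves outside care unrestricted but has its changes assessed. These changes can be reported by arm or shown in the explanatory models.
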